## **Disease Management for Coronary Artery Patients**

**Clinical Trial Register Number: NCT04556006**

**Ethics Committee Approval Date: June 6, 2018**

**Document Date: June 17, 2021**

### **Study Protocol**

#### **Setting and samples**

This study was planned as a single-blind randomised controlled trial with pretest–posttest and followed the guidelines of the Consolidated Standards of Reporting Trials (CONSORT) statement. The population of the study was composed of the patients diagnosed with coronary artery disease (CAD) staying in cardiology clinic of a State Hospital in Southeast Anatolia Region, Turkey (March, 2019–March, 2020). The sample size of the study was determined according to the result of the power analysis. The minimum sample size required for the difference to be significant in terms of compliance questionnaire (CQ) scores in patients who received and did not receive training was determined to be at least 26 patients in each group ( $\alpha = .05$ ,  $1 - \beta = .80$ , effect size = .80). The patients, who were aged between 18 and 79, were diagnosed with CAD for at least 2 months, had no hearing and vision problem, had no perception and expression deficiency, were not diagnosed with any psychiatric dis-ease and were voluntary to participate in the study, were included in the study. A total of 74 patients meeting the inclusion criteria (37 in the intervention group and 37 in the control group) were included in the sample. However, the study was terminated within the scope of COVID-19 pandemic measures that started abroad and affected Turkey too. The sample of the study consisted of 58 patients (30 in the intervention group and 28 in the control group) whose data were completely collected until the pandemic period.

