### **Randomisation**

The patients informed at the beginning of the study were randomised into the intervention and control groups. Randomisation was performed using random numbers produced in the computer (SPSS version 20 software) by a statistician who had no contact with the participants and did not participate in the study. All patients participating in the study were blinded during the randomisation process but the researchers were not blinded due to the nature of the intervention research. The patients in the control group continued to receive standard care by being unaware that they were in a training programme about treatment adherence in CAD. On the other hand, the patients in the intervention group were invited to participate in a training programme on treatment adherence in CAD.

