### **First stage**

Personal Information Form and Compliance Questionnaire were applied to all patients in both groups. After anthropometric measurements, FR score was determined. The data collection forms were filled with the patients using face-to-face interview technique. The data collection process lasted for approximately 10–15 min. After the data collection, the patients in the intervention group were trained. The patients in the control group were given only standard care protocol by clinicians. During study, no training programme was given to the patients in the control group by researcher but they received a ‘Coronary Artery Disease Adherence Guide’ end of study.

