### **Second stage**

12 weeks after the first interview, the patients were interviewed again face-to-face interview technique and the forms and measurements applied initially were repeated. The content of the collected data was the same as first stage.

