obtained and the contact information of the researcher was also given to the patients. In order to consolidate the information given, the training guide was given to the patients in the intervention group. After the training, the patients in the intervention group were contacted again in the 2nd week by using face-to-face interview and in the 4th– 8th and 12th weeks by phone calls. Training in the first meeting took approximately 30– 40 min, each of the next four interviews took approximately 10– 15 min. During these telephone interviews, the questions of the patients, if any, were answered and the problems they faced regarding the treatment adherence were tried to be solved. In the last interview, an appointment day was determined to meet face-to- face at home, workplaces or hospital according to the preferences of the patients. During the appointment day, personal information form and CQ were filled again. Last meeting took approximately 20– 30 min. The patients in the control group received only the standard care protocol provided by the clinicians. After the collection of post-test data, the content of the training was also explained to these patients and the study was completed by giving them the training guide.

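### The between-arm CQ comparison is not adjusted for baseline CQ, which costs precision and leaves the estimate open if any of the 16 exclusions depended on baseline adherence

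*Combined protocol and SAP*

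**What the plan says.** The Setting and samples section gives three facts in sequence.

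- Allocation: "A total of 74 patients meeting the inclusion criteria (37 in the intervention group and 37 in the control group".
- The stop: "the study was terminated within the scope of COVID-19 pandemic measures that started abroad and affected Turkey too".
- The analysed sample: "58 patients (30 in the intervention group and 28 in the control group) whose data were completely collected until the pandemic period".

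That the 74 were randomised follows from the arm labels together with the Randomisation section: "The patients informed at the beginning of the study were randomised into the intervention and control groups". CQ was measured before training (First stage: "Personal Information Form and Compliance Questionnaire were applied to all patients in both groups") and once more afterwards (Second stage: "12 weeks after the first interview, the patients were interviewed again face-to-face interview technique").

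The Data analysis section takes its p-values for continuous variables from a repeated-measures general linear model, with group between patients and time (initial, week 12) within patients. It reports group, time and group × time, and names none of them as the main contrast. It also lists t and Mann–Whitney tests for two-group comparisons. It lists no baseline covariate and states no missing-data assumption. No section counts the 16 excluded patients by reason or by follow-up due date.

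**The concern.** With two time points, the group × time test is algebraically a two-sample comparison of change scores. It takes full account of baseline only if the slope of the 12-week score on the baseline score is 1. If both visits have the same SD, that slope is the pre-post correlation r. When r is below 1, subtracting the whole baseline overcorrects and adds noise.

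Two things are at stake. The first is precision, which is lost whatever the reason for the exclusions. The second is robustness. Membership of the analysed set was decided after randomisation, by completeness of data. If completeness depended on baseline CQ, the arms of the analysed set could differ at baseline by more than chance, and the change score would carry regression to the mean into the treatment contrast. Conditioning on baseline CQ deals with that case.

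**Working it through.** **Inputs from the document.** Alpha .05, power .80, effect size .80, at least 26 per group; 37 + 37 allocated; 30 + 28 analysed; study window March 2019 to March 2020; 12-week follow-up. The document does not give the pre-post correlation r, so .3, .5 and .7 are assumed. Results are in SD units of CQ, with equal SD at both visits.

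**1. The plan's own figure.** A two-sided two-sample t test at effect size 0.80 has 79.1% power with 25 per group and 80.7% with 26, so 26 is reproduced. With 30 and 28 the same test has 84.9% power. The analysed number exceeds the planned minimum (58 against 52), so sample size is not the issue.

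**2. Exclusions.** 74 − 58 = 16 (21.6%): 7/37 = 18.9% in the intervention arm and 9/37 = 24.3% in the control arm, Fisher exact p = .78.

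**3. Precision.** Let f = 1/30 + 1/28 = 0.0690.

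- Group × time (change score): SE = √(2(1 − r)f)
- Adjusted for baseline: SE = √((1 − r²)f)
- Ratio: √((1 + r)/2)

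| Assumed r | SE, group × time | SE, adjusted | Reduction |
|---|---|---|---|
| .3 | 0.311 | 0.251 | 19% |
| .5 | 0.263 | 0.228 | 13% |
| .7 | 0.204 | 0.188 | 8% |

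These formulas ignore the small cost of estimating the slope. Simulated SEs at r = .5 under random loss were 0.264 and 0.231, a reduction of 1 − 0.231/0.264 = 12.5%. If the 0.80 refers to the SD of the 12-week score, power with 30 and 28 is about 71.5% unadjusted against 88.0% adjusted at r = .3, 84.9% against 93.2% at r = .5, and 97.1% against 98.7% at r = .7.

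**4. Robustness to loss related to baseline.** Simulation with 20,000 runs: 37 per arm, 7 and 9 lost, true effect 0.80, r = .5. The chance of loss rises as baseline CQ falls, with weight exp(−c × baseline in SD). Monte Carlo error is 0.002.

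| Loss depends on baseline in | c | Group × time | ANCOVA, same 58 |
|---|---|---|---|
| neither arm | 0 | 0.80 | 0.80 |
| both arms | .5 / 1.5 | 0.82 / 0.83 | 0.80 / 0.80 |
| intervention arm only | .5 / 1.5 | 0.75 / 0.68 | 0.80 / 0.80 |
| control arm only | .5 / 1.5 | 0.87 / 0.95 | 0.80 / 0.80 |

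The ANCOVA column follows from the set-up: loss depends on baseline alone, and the outcome is linear in baseline with a common slope. The table shows what adjustment protects against. It does not show what happened in this trial.

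**5. Can the stop explain all 16?** Assume even accrual over W weeks up to the stop, with the last enrolment L weeks before it. The expected number not yet at 12 weeks is 74 × (12 − L)/(W − L).

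- L = 0, W = 48/52/56: 18.5, 17.1, 15.9. All 16 are covered.
- L = 4, W = 48/52/56: 13.5, 12.3, 11.4. On a binomial count with SD 3.1 to 3.3, the probability of 16 or more is .10 to .26, so 16 is not surprising here either.

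The Standard care protocol section adds that for the intervention arm "In the last interview, an appointment day was determined to meet", so the post-test could fall after week 12. If that added 2 weeks in both arms (assumption), the L = 4 case gives 74 × 10/44 = 16.8 down to 74 × 10/52 = 14.2.

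**6. Does restoring the 16 baselines help?** In five simulated data sets, a constrained-baseline maximum-likelihood model on all 74 matched ANCOVA on the 58 to five decimals. The gain comes from the adjustment, not from the extra baseline records.

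**The case against.** The strongest reply is that the planned model is valid. Baseline CQ is already in it as the first repeated measure, randomisation makes the change-score contrast unbiased, and ANCOVA against change score is partly a matter of preference. The validity part stands, so this is not an error in the analysis. But the precision gain uses data already in hand and does not depend on any bias being present.

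A reader might infer something stronger: that dropping 16 of 74 patients biased the result, or that an analysis of all 74 is required. The documents do not support either reading. They give the COVID-19 stop as the reason, and step 5 shows that it can account for all 16. The loss counts are similar in the two arms, although similar counts cannot exclude different reasons. The extreme estimates of 0.68 and 0.95 need selection in one arm only, which nothing in the text indicates. With selection in both arms the shift is 0.02 to 0.03 against an SE of about 0.26. Moving to all 74 leaves the estimate where ANCOVA on the 58 puts it.

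Two further points stand. Treating group × time as the between-arm CQ contrast is an inference, since the plan names no main contrast; that is a reason to name one. And the document is dated June 2021, after the stop, so any change of model is post hoc and should say so.

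**Conclusion.** The point holds as one of efficiency and robustness. Baseline adjustment reduces the SE of the between-arm CQ difference by about 19%, 13% and 8% at r = .3, .5 and .7, assuming equal SDs at the two visits and a linear relation. It also removes bias from exclusions that depended on baseline CQ, given a linear outcome model with a common slope in both arms. It does not help if exclusion depended on the unobserved 12-week score. No bias is shown, and the exclusions are consistent with the stop alone. The missing count of patients not yet due is a reporting gap that would settle how much the second benefit matters.

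**What to change.** 1. Estimate the between-arm CQ difference at 12 weeks by ANCOVA on baseline CQ in the 58, each patient in the assigned arm, with a 95% confidence interval. Name this as the between-arm CQ contrast.
2. Keep the group × time model as a supporting analysis, labelled as completers only.
3. State that the change was made after data collection, and report both results.
4. From first-interview dates and the stop date, report by arm how many of the 16 were not yet due.
5. Optional: a constrained-baseline mixed model on all 74, with its missing-at-random assumption stated. It needs the 16 baseline records and should give the same estimate.

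The cost is some wording, a small re-analysis of data already collected, and a post hoc label. No new patients or measurements are needed. If r is high, the gain in precision is modest.

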## **Data collection tools**

The data of the participants were collected by using personal information form, anthropometric measurements, Framingham risk score and compliance questionnaire.

### **Personal information form**

It was prepared by the researchers by reviewing the related literatures. In this form, there were questions investigating the patients' socio- demographic characteristics, anthropometric measurements and CAD risk factors.

### **Compliance questionnaire**

Compliance Questionnaire (CQ) is a form allowing to investigate 11 different areas such as the use of medication causing maladaptation in disease management in individuals with chronic illnesses, diet, weight loss, limiting physical activity, exercise, coping with stress, alcohol use, smoking, sexual activity problems, caffeine intake and working/job life. It was developed by Marston in 1969. In the form allowing Likert-type evaluation, the participant is expected to select one of the options 0 (never), 1 (very rarely), 2 (sometimes), 3 (most of the time) or 4 (always) while expressing his/her adherence level for each adaptation area. The scores corresponding to the given expression are summed, and CQ score for each participant is determined. The maximum score is 44. High score signifies an increase in the adherence level to the disease. In the validity and reliability study, internal consistency of CQ was determined as Cronbach's Alpha value .56 and intraclass correlation coefficient value .69. In this study, the internal consistency Cronbach's Alpha value of the responses given to CQ was found as .701.

### **Anthropometric measurements**

Anthropometric measurements (height, weight, waist circumference and hip circumference) were performed by the researcher when the patients had thin clothes that would not change their weights. In repeated measurements, attention was paid to ensure that the clothes were in similar weights. For example, the patient, who wore a thin pyjama in the first measurement, was asked to change his clothes if he/she wore a thick sweater in the second measurement. In addition, care also given during the weight measurements that the patients were hungry and did not need defecation/micturition. Weight measurements were made using a digital scale showing decimal values and measuring weights in kilograms. While measuring the height, waist circumference and hip circumference, a plastic tape measure divided by 0.1 cm intervals without stretching feature was used. In the measurements made with tape measure, the patients were asked to stand upright position and leave their abdomen freely by not pulling in. The obtained data were recorded in the related form.

### **Randomisation**

The patients informed at the beginning of the study were randomised into the intervention and control groups. Randomisation was performed using random numbers produced in the computer (SPSS version 20 software) by a statistician who had no contact with the participants and did not participate in the study. All patients participating in the study were blinded during the randomisation process but the researchers were not blinded due to the nature of the intervention research. The patients in the control group continued to receive standard care by being unaware that they were in a training programme about treatment adherence in CAD. On the other hand, the patients in the intervention group were invited to participate in a training programme on treatment adherence in CAD.

### **Data collection**

The data collection process of the study was carried out in two stages using data collection tools.

### **First stage**

Personal Information Form and Compliance Questionnaire were applied to all patients in both groups. After anthropometric measurements, FR score was determined. The data collection forms were filled with the patients using face-to-face interview technique. The data collection process lasted for approximately 10–15 min. After the data collection, the patients in the intervention group were trained. The patients in the control group were given only standard care protocol by clinicians. During study, no training programme was given to the patients in the control group by researcher but they received a ‘Coronary Artery Disease Adherence Guide’ end of study.

### **Second stage**

12 weeks after the first interview, the patients were interviewed again face-to-face interview technique and the forms and measurements applied initially were repeated. The content of the collected data was the same as first stage.

### **Standard care protocol**

In the standard care protocol provided by clinicians, no printed/visual material was provided to the patients, only verbal information was given. In this protocol, only unstructured basic information about the disease, treatment and risk factors is given to the patients. However, behavioural changes in patients are not followed. Standard care protocol was applied by clinicians to all patients participating in the study. In addition, coronary artery disease training programme was applied to the patients in the intervention group by first researcher.

The training programme is not only more structured training than the standard care programme but also includes patient follow-up at certain periods. Thus, the effect of the given education and follow-up on patient behaviour is monitored. A training guide named 'Coronary Artery Disease Adherence Guide' was given to the patients in the intervention group. This training guide includes information about basic information about CAD, risk factors (hypertension, diabetes, obesity, smoking, alcohol, stress and sedentary life), adherence with treatment (drug use and clinical check-up appointments) and healthy lifestyle behaviours (exercise and weight control). The training guide was prepared by the researchers by bringing guides prepared by national and international organisations about the subject and the related literature together. While preparing the training guide, attention was paid to use plain language and 16 font size so that patients could easily read and understand. It was prepared in a comprehensive enough way to meet the patients' need for information about disease, treatment process, risk factors and coping mechanisms. In addition, the guide was put into final form by obtaining opinions of different experts from fields of internal medicine nursing, psychiatric nursing, physiotherapy and rehabilitation, nutrition and dietetics for independent assessment. The training programme was applied to patients in intervention group by the first author who also works as an academic nurse. After the nurse explained the information in the training guide for each patient as a standard, the question / answer part started. During the training, patients' relatives were allowed to be in the room if they wanted and patients/their relatives were encouraged to ask questions. The questions asked were answered in accordance with the explanations in the training guide. Exercises and relaxation movements that the patients had difficulty understanding were demonstrated by the researcher. Afterwards, the patient was asked to repeat these movements. During the study, the researcher examined the patients' behaviours, encouraging the correction of the wrong ones and the continuation of the correct ones. The contact information of the patients was

obtained and the contact information of the researcher was also given to the patients. In order to consolidate the information given, the training guide was given to the patients in the intervention group. After the training, the patients in the intervention group were contacted again in the 2nd week by using face-to-face interview and in the 4th– 8th and 12th weeks by phone calls. Training in the first meeting took approximately 30– 40 min, each of the next four interviews took approximately 10– 15 min. During these telephone interviews, the questions of the patients, if any, were answered and the problems they faced regarding the treatment adherence were tried to be solved. In the last interview, an appointment day was determined to meet face-to- face at home, workplaces or hospital according to the preferences of the patients. During the appointment day, personal information form and CQ were filled again. Last meeting took approximately 20– 30 min. The patients in the control group received only the standard care protocol provided by the clinicians. After the collection of post-test data, the content of the training was also explained to these patients and the study was completed by giving them the training guide.

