### **Data analysis**

The data were investigated using IBM SPSS Statistic 20.0 program. As the descriptive statistics, frequency, percentage, mean and standard deviation were used. In the adherence control of continuous variables to normal distribution, Shapiro–Wilk test was used. While independent samples t test was used in the comparison of two independent groups having normal distribution, Mann–Whitney u test was used for the non-normal distributed data. In the determination of the correlation between categorical variables, Chi-Square test was used. Since measurements were repeated twice (initial–12thweeks), p- values for continuous variables are obtained from general linear model repeated measures analysis. The group was used as the between-subject factor, and time as the within-subject factor. Mean values with their 95% confidence intervals and p- values for group, time and group × time interaction

were reported. In this way, type I error rate within- and between-groups variation was controlled. Effect size (Cohen's  $d$ ) was used for measure of the magnitude of the experimental effect. It was suggested that  $d = 0.2$  be considered a 'small' effect size, 0.5 represents a 'medium' effect size and 0.8 a 'large' effect size. The larger the effect size the stronger the relationship between two variables. Statistical significance level was accepted as  $p < .05$ .

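### Do the two accounts of the 12-week post-test show that the arms were assessed differently?

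*Combined protocol and SAP*

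**What the plan says.** The combined protocol and SAP describes the post-test in two places.

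- **First stage and Second stage.** At baseline both groups have the personal information form, the compliance questionnaire (CQ), anthropometry and a Framingham score. On time, First stage says: "The data collection process lasted for approximately 10–15 min". Second stage then says: "12 weeks after the first interview, the patients were interviewed again". It adds that the baseline forms and measurements were repeated, and: "The content of the collected data was the same as first stage". It names no arm and gives no duration, place or visit window.
- **The training-programme text under Standard care protocol.** After listing the intervention arm's contacts, it says: "In the last interview, an appointment day was determined to meet", with the place left to the patient. It continues: "During the appointment day, personal information form and CQ were filled again". On length: "Last meeting took approximately 20– 30 min". For controls it says only that the training content was explained, and the guide handed over, once post-test data had been collected.

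Data analysis treats all patients as having one common pair of measurements, baseline and week 12 ("Since measurements were repeated twice"), and tests group, time and group × time.

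**The concern.** Three things catch the eye.

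1. The follow-up meeting in the intervention arm is given twice the time of the baseline data collection, although the content is said to be the same.
2. Only two forms are named for that meeting, so a reader may wonder whether the measurements were dropped.
3. The booking and the choice of place are described for the intervention arm alone.

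The stakes would be real if the arms had been assessed differently. The CQ is a self-expressed adherence score taken in an interview, and the section Randomisation says the researchers were not blinded. If one arm's interview followed further coaching, or took place in a different setting or at a different time, part of the group × time effect could reflect the assessment and not the training.

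**Working it through.** **The plan's only computable design figure.** Setting and samples gives a minimum that "was determined to be at least 26 patients in each group", with α = 0.05, power 0.80 and effect size 0.80. The two-sided normal approximation is n = 2(1.960 + 0.842)² / 0.80² = 2 × 7.85 / 0.64 = 24.5, which rounds up to 25. The two-sided t-test gives 25.52, which rounds up to 26, with power 0.807 at 26 per group. The figure reproduces, and the concern does not touch it.

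**Which contact is which.** The intervention arm is seen in week 2 and telephoned in weeks 4, 8 and 12. That makes four contacts, which matches the four follow-up interviews the text counts. The last interview is therefore the week-12 call, and the last meeting is the appointment fixed in it.

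**Timing.** Assume that the twelfth week runs from day 78 to day 84 and that the post-test is due on day 84. The interval from call to visit can then be 84 − 84 = 0 to 84 − 78 = 6 days, with no conflict with Second stage. What is missing is a window, and it is missing for both arms.

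**Duration.** Subtracting the stated ranges gives a smallest gap of 20 − 15 = 5 minutes, a largest of 30 − 10 = 20, and 25 − 12.5 = 12.5 at the midpoints. The subtraction does not compare like with like:

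- The 10–15 minutes belongs to the baseline data collection. It follows directly on the sentence about completing forms by interview, so it may or may not include the anthropometry. Second stage gives no time of its own.
- The 20–30 minutes is the length of a whole meeting, possibly at the patient's home or workplace.
- The document separates these quantities at baseline too: data collection takes 10–15 minutes, and training at the first meeting takes a further 30–40.

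**Content.** Four statements, read together, cover most of the question:

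| Section | What it settles |
|---|---|
| Personal information form | The form includes anthropometry and risk factors, so naming two forms does not imply that measurements were left out |
| First stage | The Framingham score is something determined after measurement, not a form to fill in; its absence from a sentence about filling in forms is weak evidence |
| Second stage | Baseline forms and measurements repeated, same content, no arm singled out |
| Anthropometric measurements | Clothing, fasting and scale conditions stated without restriction to an arm |

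**Order.** The controls' post-test data were taken before they received any of the training content. Their CQ scores are therefore not affected by it.

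**What the text does not supply.** It gives no visit window for either arm. It gives no booking route, place or visit length for the 28 analysed controls. For the 30 analysed intervention patients, it does not say what else the last meeting contained or whether that came before the CQ.

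**The case for a change.** The best argument for acting is that an interview-based score taken by unblinded staff is the setting in which a reader most needs to see identical procedures, and the document does not let the reader check them. Order is stated for controls but not for the intervention arm. The training text says the researcher encouraged the correction of wrong behaviours during the study, so it is fair to ask whether that continued at the final visit before the CQ was filled in. Weighing at a home or workplace is also harder to standardise than in hospital. A sentence or two and a descriptive table would cost little.

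The omission stands as described. It is an omission only: no passage says or implies that controls were booked, visited or interviewed differently, and Second stage, read naturally, covers both arms on mode, nominal timing and content. The intervention arm was also due a call about adherence problems in week 12 by design, so late contact with that arm is part of the programme being tested. The lack of blinding is a separate limitation, already declared, and stating the place or length of the control visits would not lessen it.

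**Conclusion.** No change to the plan is needed. The two accounts can be read together without contradiction: one states the common post-test, and the other adds how it was arranged in the arm whose contacts it is narrating. The residual gap is one of reporting. It covers the visit window in both arms, the booking, place and length of the control visits, and the full content of the intervention arm's last meeting.

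No bias is shown and no effect on a result can be calculated. The only remedy would be wording, plus an optional descriptive table if dates and places were recorded. The document describes a completed study, so neither would alter what was done, the repeated-measures model or the sample size.

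This rests on two readings: that Second stage applies to both arms, since it follows a section on all patients in both groups and names no arm, and that the 20–30 minutes is the length of the meeting and not of data collection alone. If records showed that the control visits differed in timing or setting, the question would reopen. Nothing in the document points that way.
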